## **H.3 Schedule of Measurements**

Section N details the schedule of measurements. Data will be collected preoperatively at the initial screening visit, during the perioperative period, at the follow-up appointment (2 weeks following discharge), and at 1 month, 3 months, and 6 months (by telephone or mail).

## **I. DATA COLLECTION**

All data collection following surgery will be performed by research staff other than the study surgeon. This will reduce bias by maintaining masking in data collection of outcome measures. All research staff will be trained and certified to perform data collection procedures. Allowable windows for timed evaluations are specified in Section N and include a one-week window on each side of the postoperative visit planned at 2-3 weeks. The assessments at 1-month, 3-months, and 6-months will take place by mail and will not require a visit to the clinical site.

### **I.1 Demographics, Medical History, and Physical Examination**

#### **a. History**

- i. Age
- ii. Sex

- iii. Previous medical history
- iv. Prior thoracic procedures
- v. Primary diagnosis
- vi. Previous thoracic chemotherapy or radiation
- vii. Planned procedure
- viii. Comorbidities will be collected using the Charlson Comorbidity index collected at baseline

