### **D. OUTCOME MEASURES**

The primary outcome measure for specific aim 1 will be the quality of life and patient satisfaction as measured by post-operative survey instruments.

Secondary Outcomes for specific aim 1:

- Complications following surgery (jejunal tube)
- Length of stay
- Costs

The primary outcome for specific aim 2 will be the occurrence of post-operative complications such as: atrial fibrillation, delirium, anastomotic leak, pneumonia within the 30-day post-operative time frame.

Secondary Outcomes for specific aim 2:

- Readmission rates and costs of care.

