**J. STATISTICAL AND DATA MANAGEMENT CONSIDERATIONS**

**For the specific aims:**

Specific Aim 1: Quality of Life measurements will be compared at 6 months, using descriptive statistics.

Specific Aim 2: Calories will be compared between groups.

**For the secondary aims:** Height and weight will be compared between groups at 30 days and 6 months.

**Sample size justification:** This was measured with the possible recruitment pool and differences between groups.

**Interim analysis:** At 50% recruitment or three years.

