**Randomization:**

This study will randomize eligible patients to receive post-operative tube feeding for 1 month or standard post-operative care in a one-to-one fashion. Patients will be randomized using a blocked randomization technique in order to ensure equal sample sizes across groups. [name] – is this correct? The study statistician ([name]) will generate the randomization assignment table for the study's data manager. The investigators will call the data manager for the treatment assignment when a patient has been fully consented and is determined to be eligible for study enrollment.

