## N. TIMELINE OF VISITS, MEASURES AND FORMS:

Table 1 Timeline of Visits and Data Collection

	Screening & Enrollment	Inpatient (post-op)	Follow-up (Clinic- 2 weeks)	1 Month	3 Months	6 Months	Specific Aim (1 or 2)
Eligibility	X	X*					1/2

Consent	X						1/2
Demographics	X						1/2
Charlson Comorbidity Index	X						1/2
Quality of Life Assessment	X		X	X	X	X	1
Randomization		X					
Adverse Events			X	X	X	X	2
Hospital LOS			X				1/2
Costs						X	1/2

\*assess for continued study eligibility prior to randomization

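### Section J contains no analysis of complications or readmission (Aim 2) and uses none of the baseline risk factors already collected; when the analysis is added, a small covariate set should be fixed in it (minor)

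*Combined protocol and SAP*

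**What the plan says.** Section I.1 lists the baseline history items. They include age, "Previous thoracic chemotherapy or radiation" as one item, and comorbidity: "Comorbidities will be collected using the Charlson Comorbidity index collected at baseline". Table 1 in Section N has a row for the "Charlson Comorbidity Index" and one for demographics. Both are collected at screening and tagged to both aims.

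Section D names complications "within the 30-day post-operative time frame" as the Aim 2 primary outcome, with readmission and costs as secondary.

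Section J then gives three comparisons. For Aim 1: "Quality of Life measurements will be compared at 6 months, using descriptive statistics". For Aim 2: "Specific Aim 2: Calories will be compared between groups". A third line, on secondary objectives, adds: "Height and weight will be compared between groups at 30 days and 6 months". No model, covariate, stratum or subgroup is named.

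On allocation, Section J says: "Patients will be randomized using a blocked randomization technique in order to ensure equal sample sizes across groups". No stratification factor is given. The sample size in Section K is a placeholder, and no event rate, alpha or power appears anywhere.

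**The concern.** Two things are missing, and they are of unequal weight.

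The first is the analysis itself. Aim 2 asks whether tube feeding after discharge changes complications and readmissions, and Section J provides no comparison of either. Its Aim 2 line concerns calories, which Section D does not list as an outcome. As written, the plan cannot answer Aim 2.

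The second is that nothing in the design or analysis takes account of baseline risk. Blocking controls the size of the arms, not their composition. If the trial is small, the arms may differ by chance in age, comorbidity or prior treatment. If those factors predict complications, part of the variation in outcome could be removed with data already in hand. The trial is also unblinded (Section C), so covariates chosen after outcomes are known would carry less credibility than a set fixed beforehand.

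**Working it through.** The plan has no figure to reproduce. Everything numerical below is an illustration under stated assumptions.

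**Step 1: outcomes against analyses.**
- Complications: defined in Section D as Aim 2 primary; no analysis in Section J.
- Readmission: defined in Section D as Aim 2 secondary; no analysis in Section J.
- Age, Charlson index, prior chemotherapy or radiation: collected under Section I.1; absent from Section J, including its randomisation paragraph.

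**Step 2: possible gain in power.** Assumed inputs: two-sided alpha 0.05, 1:1 allocation (the ratio is from Section J), complication rates 40% and 25%, and 70 per arm. The last is the upper end of the 12 to 70 per group that Section B reports for earlier trials. R² is the share of outcome variance explained by the covariates.

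Unadjusted power = Φ[(d − 1.96·SE₀)/SE₁], where
- d = 0.15
- SE₀ = √(2 × 0.325 × 0.675/70) = 0.0792
- SE₁ = √((0.40 × 0.60 + 0.25 × 0.75)/70) = 0.0781

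This gives 47.4%. Adjustment is approximated by an effective size of 70/(1 − R²) per arm. The number per arm for 80% power is 152 unadjusted, and 152 × (1 − R²) adjusted, rounded up.

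| R² | effective n per arm | power | gain (points) | n per arm for 80% |
|---|---|---|---|---|
| 0 | 70 | 47.4% | – | 152 |
| 0.02 | 71.4 | 48.1% | 0.7 | 149 |
| 0.05 | 73.7 | 49.4% | 2.0 | 145 |
| 0.10 | 77.8 | 51.5% | 4.1 | 137 |
| 0.20 | 87.5 | 56.4% | 9.0 | 122 |

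**Step 3: the cost of fitting covariates.** The formula above ignores that cost, so it was checked by simulation: 1,500 trials per setting, control rate 40%, treated rate about 22% to 25%, three covariates. The model was a linear risk-difference regression with robust standard errors, which serves as a guide to the standardised logistic estimate and is not identical to it. Ratio of adjusted to unadjusted variance of the risk difference:

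| R² | 35 per arm | 70 per arm |
|---|---|---|
| 0 | 1.04 | 1.02 |
| 0.02 | 1.04 | 1.00 |
| 0.075 | 0.98 | 0.95 |
| 0.17 | 0.88 | 0.84 |

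A ratio above 1 is a loss. Weak covariates give nothing at 70 per arm and cost about 4% in variance at 35.

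**Step 4: chance imbalance.** Take a binary factor present in 60% of patients (assumed). The SD of the difference between arms is √(2 × 0.6 × 0.4/n), which is 9.8 points at 50 per arm and 6.9 at 100. The exact binomial probability of a difference strictly above 10 points is about 26% at 50 per arm and 13% at 100. The normal approximation gives 31% and 15%.

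To see what such an imbalance does, suppose the factor raises complication risk by 20 points (assumed). A 10-point imbalance then moves the estimated effect by 0.10 × 20 = 2 points. The standard error of the risk difference at 50 per arm is √((0.40 × 0.60 + 0.25 × 0.75)/50) = 9.2 points. The shift is small against the ordinary sampling error.

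**The case against.** The strongest case against is that an unadjusted comparison of randomised arms is valid. Randomisation prevents systematic bias, and the unadjusted confidence interval already allows for chance imbalance. Adjustment is therefore a matter of efficiency, with a benefit between nil and modest. All of this stands, and it is why the point is minor.

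Four stronger readings are tempting, and the documents do not support them.

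- A reader might infer that planned complication and readmission comparisons are losing precision. No such comparison is planned, adjusted or unadjusted.
- A reader might infer that these covariates are collected for Aim 2 and then wasted. Table 1 tags the Charlson index and demographics to both aims, and prior treatment has no row of its own. Under Section H the history forms come from a companion protocol whose data are shared. Baseline data also serve to describe the sample.
- A reader might take Section B as stating that comorbidity and prior treatment drive complications. It says only that patients' condition may be reduced by chemo- and radiotherapy and by dysphagia. It does not mention comorbidity, and no section quantifies the link of any of the three factors with the Aim 2 outcomes.
- A reader might conclude that imbalance could readily hide or create a feeding effect. Step 4 of the working shows that a sizeable imbalance in a fairly strong factor moves the estimate by much less than one standard error.

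What survives is that Aim 2 needs an analysis, and that the covariates should be settled when it is written, before outcomes are seen.

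**Conclusion.** The point holds in limited form, and its severity is minor. That Section J omits complications and readmission, and that no analysis or stratum uses the three collected risk factors, can be read directly from the documents and rests on no assumption.

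The size of the benefit does rest on assumptions, because the plan gives no sample size, event rate, covariate prevalence or R². At 70 per arm with 40% against 25%, it is about 1 to 4 power points for R² of 0.02 to 0.10. The simulation suggests no gain at the lower end of that range, and a variance loss of about 4% with weak covariates at 35 per arm.

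Adjustment deals with chance imbalance only. It also leaves a separate problem untouched. Complications are counted over 30 post-operative days, while Section F opens the envelope before discharge or at post-operative day 8, so the outcome can include events that precede randomisation. No baseline covariate corrects that.

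**What to change.** In Section J, add a between-arm comparison of complications and another of readmission:

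1. Fit a logistic model for each, with arm, Charlson score, age, and prior thoracic chemotherapy or radiation (coded as the single item collected). Fix the covariates before any outcome is seen.
2. Report the standardised (marginal) risk difference with its 95% CI, and the unadjusted risk difference alongside.
3. State in advance a rule for reducing the covariate set if events are few, including the order in which covariates are dropped. This matters because neither the sample size nor the expected event count is known.

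The cost is a short addition to the analysis section, with no new data. The downside is a small loss of precision if the covariates prove weak in a small trial; the reduction rule limits it, and the unadjusted result makes it visible. Which complications count, relative to the time of randomisation, should be settled separately before this model is applied.

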**b. Physical Examination**

- i. Height
- ii. Weight
- iii. BMI

**J. STATISTICAL AND DATA MANAGEMENT CONSIDERATIONS**

**For the specific aims:**

Specific Aim 1: Quality of Life measurements will be compared at 6 months, using descriptive statistics.

Specific Aim 2: Calories will be compared between groups.

**For the secondary aims:** Height and weight will be compared between groups at 30 days and 6 months.

**Sample size justification:** This was measured with the possible recruitment pool and differences between groups.

**Interim analysis:** At 50% recruitment or three years.

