**Protocol 01**

**06/16/2014**

## A. STUDY AIMS

Specific Aim 1: To determine if routine dietary supplementation with enteral tube feeding affects recovery and quality of life after esophagectomy. Medicare rules only pay for enteral supplements (tube feeding) if the patient needs alternative feeding for greater than 3 months. Many insurers have adopted these rules, without evidence in post-operative patients.

- We hypothesize that routine post-operative supplementation will enhance patients recovery and quality of life, by increasing the time of adequate nutrition.

Specific Aim 2: To determine the occurrence of common complications and readmissions post-operatively between patients who are routinely discharged with tube feeding and those that are not. If patients are not discharged with tube feeds, they must obtain all of their nutrition by mouth, which may be difficult in the early post-operative period.

- We hypothesize that routine use of tube feeding may reduce the occurrence of complications.

The secondary aims of this randomized clinical trial are:

- To compare costs of care between groups.
- To assess how length of stay (LOS) and readmission rates are affected by routine use of tube feeding, as well as costs of care.
- Rates of occurrence of tube feeding or jejunal tube-specific complications

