## B. BACKGROUND AND SIGNIFICANCE

Nutritional support is taking on an increasing focus in peri-operative surgical care. It is particularly important in esophageal resection, which is a high-risk operation in a patient population whose pre-operative condition may be reduced due to pre-operative chemo- and radio-therapy, as well as dysphagia from the cancer. Post-operatively, patients are routinely cleared to take nutrition by mouth once an esophagram is done post-operative day 7 and shows no abnormality.

Tube feeding should be at goal by day 7, but is discontinued once patients are discharged, as long as they are able to eat, i.e., do not have evidence of anastomotic leak or other serious complications. The amount patients are able to eat is frequently variable, and is not well recorded prior to or after discharge. There may be a dip in calories consumed, which if severe, will lead to readmission for

hydration, failure to thrive, or possibly the development of a post-operative complication.

Currently all patients are discharged with the jejunal feeding tube placed at the operation, just in case they are unable to eat post-operatively due to an unforeseen complication. Since many insurers and Medicare require patients to pay for tube feeding needed for less than three months (~\$800/month and up, plus the services of a home health nurse), we do not routinely require patients use the feeding tube once discharged.

For esophagectomy specifically, and upper gastro-intestinal surgery in general, there is very limited literature looking at this question. Small randomized studies have not shown a benefit to routine tube feeding, although the numbers were very small, ranging from 12 to 70 in each group. Furthermore, the duration of tube feeding averaged 14 days, and even in the groups being fed enterally, were not meeting caloric needs in the period studied.

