### **C. STUDY SCHEMA**

Patients will be evaluated for surgery by the study surgeons. Patients scheduled to undergo an elective esophagectomy and who meet inclusion criteria (See Section E.1) will be approached for enrollment. Written informed consent will be obtained from all enrolled patients (see Appendix B). Pre-operative Quality of Life Survey will be obtained using the EORTC QLQ-C30 (see attached). Patients will then be randomly assigned to either routine post-operative tube feeding for 1 month, or usual practice, tube feeding to continue in the hospital until the patient is taking adequate nutrition by mouth at POD#8, or upon discharge. Since this study cannot be blinded, patients that cannot take nutrition by mouth at POD#8, or are tube feeding dependent on discharge will not be included in analysis.

Figure 1. Illustrates the study design

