## **F. RANDOMIZATION AND MASKING**

Randomization envelopes will be created at the start of the study. Each envelope will be opened prior to discharge or at POD#8 if patients are able to take adequate nutrition by mouth, to determine if post-operative tube feeding will be continued or not.

By consenting to the study, patients agree to continue tube feeding for at least 50% of caloric needs for 1 month post-operatively. Cross-over after randomization will be permitted for patient condition, although once randomized, patients will be analyzed by the original group.

- A copy of the signed research consent form must be included in the patient's hospital chart.

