## **H. MEASUREMENT**

The assessment instruments that will be used for specific aim 1:

1. EORTC QLQ-C30, Quality of life in cancer patients

The complications assessment instruments that will be used for specific aim 2:

1. HUM00012731 data collected around the time of operation and post-operative visit.
2. Long-term data from HUM00012731

Patients will also be invited to enroll in the “Patient outcomes following esophagectomy for benign and malignant disease” HUM00012731, a study in which the PI ([name]) is also a co-investigator. To minimize patient burden, the baseline preoperative assessment and the evaluation for quality of life will be performed according to the protocol outlined in HUM00012731. Demographics and history forms HUM00012731 will only be administered once preoperatively. This data will then be shared to support the study aims of this protocol to minimize patient inconvenience. In the event, that a patient does not wish to be co-enrolled in HUM00012731, the attached forms (EORTC QLQ-C30 and Demographics and history forms HUM00012731) will be administered by the Thoracic Surgery Clinical Coordinator, who will be trained and added to the HUM000XXXXX study protocol, at the scheduled time points outlined in Section N.

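### The Aim 1 primary comparison is planned only as descriptive statistics at 6 months, with no effect estimate, confidence interval or test and no QLQ-C30 score named as primary

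*Combined protocol and SAP*

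**What the plan says.** All places are in the combined protocol and SAP.

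- **Hypothesis.** Section A expects that "routine post-operative supplementation will enhance patients recovery and quality of life".
- **Design.** Section J (Randomization) allocates one-to-one. Section F adds that "once randomized, patients will be analyzed by the original group".
- **Primary outcome for Aim 1.** Section D names "the quality of life and patient satisfaction as measured by post-operative survey instruments".
- **Instrument.** Section H lists one for Aim 1: "EORTC QLQ-C30, Quality of life in cancer patients". Section C has it completed before surgery.
- **Timing.** Section H.1 places the primary quality-of-life assessment before surgery and at the post-operative visit. Table 1 in Section N schedules it five times: at screening, at the 2-week clinic visit, and at 1, 3 and 6 months.
- **Analysis.** Section J has one sentence: "Quality of Life measurements will be compared at 6 months, using descriptive statistics".
- **Rules that bear on the analysis.** Section C leaves some patients out of the analysis: those who cannot eat by post-operative day 8 and those who depend on tube feeding at discharge. Section K replaces patients who drop out or are lost to follow-up. Section J sets an interim analysis: "At 50% recruitment or three years".

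**The concern.** A randomised trial with a directional hypothesis needs a planned estimate of the difference between groups and a statement of its uncertainty. Summaries by group supply neither. The QLQ-C30 is named only as a whole instrument and is given at four post-operative times, so several scores and several time points could each be presented as the primary result.

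At stake is whether the primary question gets a pre-specified answer. A reader could work out an interval from published means and standard deviations. By then, however, the score, the time point and the method would have been picked with the results in view.

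**Working it through.** The plan has no figure of its own to reproduce for this analysis. Section J gives no significance level, power, target difference or standard deviation, and Section K leaves the sample size as an unfilled placeholder. The check is therefore mainly one of text.

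**1. What a primary comparison needs, set against what is given**

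| Element | Where it should appear | What is there |
|---|---|---|
| Groups compared | F, J | One-to-one, by original group |
| Score | D, H, J | Whole instrument only; no score named |
| Time point | D, H.1, J | D: none; H.1: post-operative visit; J: 6 months |
| Effect measure | J | None |
| Confidence interval or test | J | None |
| Baseline adjustment | J | None, although the pre-operative score is collected |
| Patient satisfaction | D, H, J | Part of the outcome in D; no instrument in H; no analysis in J |

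The Section J sentence is complete, so the gap comes neither from blacked-out text nor from the conversion of the PDF. The open queries left elsewhere, in J (Randomization), K and L, do not touch it. Answering them would leave it unchanged.

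**2. Time point.** H.1 carries the heading for primary outcome measures, and its post-operative visit is not the 6-month assessment in J. Section H.3 puts the follow-up appointment 2 weeks after discharge and lists 6 months separately, by telephone or mail. These are different assessments.

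**3. Analysis population.** Section C describes assignment after the pre-operative survey. Section J (Randomization) has the investigators obtain it once the patient is consented and eligible. Sections F, L and Table 1 place it later, on day 8 or before discharge. If assignment comes early, the Section C exclusion removes patients who have already been randomised, which conflicts with the Section F rule. If it comes late, most or all of those patients would never be randomised. The documents support both readings.

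**4. Scale, for context only.** Section B says of earlier randomised studies that "the numbers were very small, ranging from 12 to 70 in each group". Assume two equal groups of n, a common SD, complete scores and no adjustment. In SD units:

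- Standard error = √(2/n).
- 95% half-width = t(2n−2) × standard error.
- n = 12: √(2/12) = 0.408; 2.074 × 0.408 ≈ 0.85 SD.
- n = 70: √(2/70) = 0.169; 1.977 × 0.169 ≈ 0.33 SD.

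These are intervals at other studies' sizes. They show what a purely descriptive report would leave unstated, and they are not an estimate for this trial.

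**The case against.** The fair case on the other side has three parts.

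*A comparison is planned.* Section J does say that the groups will be compared, and that could include a raw difference in means. This stands as far as it goes: it would be wrong to infer that no comparison is intended. But the only method named is descriptive, and no measure of uncertainty accompanies it.

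*Some material is not in view.* Section H says that the quality-of-life evaluation follows a companion study's protocol, and Section C refers to an attached form. Neither is available. So the claim about satisfaction must be limited: these documents name no instrument for it. That none exists cannot be shown.

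*The harm can be overstated.* This stands. Three stronger readings are tempting, and the documents do not support them:

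- A reader might infer that the interim analysis inflates the false-positive rate. Two unadjusted looks at two-sided 5%, the first at half the information, would give about 8.3%. That needs a test which the plan does not contain, an interim look at this outcome which it does not state, and unadjusted 5% at both looks.
- A reader might infer that replaced patients are dropped from the analysis and bias it. Section K does not say so, and Sections F and L keep randomised patients in their original group.
- A reader might take the interval widths above as the size of the defect. They reflect ordinary sampling variation and would be much the same under a fully specified unadjusted analysis.

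**Conclusion.** The concern holds in this form. The sole analysis statement for the Aim 1 primary outcome chooses descriptive statistics. No section supplies an effect estimate, interval or test, or names the primary score. The outcome definition is also inconsistent over satisfaction and over the time point. As written, the trial's primary randomised question gets no pre-specified inferential answer. This must be settled before outcome data are examined, because it cannot be pre-specified afterwards.

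Its size cannot be computed. The sample size is blank, and the effect of choosing a score late depends on how many scores are considered and how they are correlated, which the documents do not give. The text finding rests on no numerical assumption. The ±0.85 and ±0.33 SD figures are context only, under the assumptions listed with them.

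**What to change.** Replace the Aim 1 line in Section J with:

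> The primary Aim 1 analysis compares one pre-named QLQ-C30 score at one pre-named time point between randomised groups, with patients analysed by original group, using a linear model adjusted for the pre-operative score. It reports the adjusted mean difference with its 95% confidence interval (and a two-sided p-value if a test is wanted). Other scores and time points are secondary.

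Then:

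- The sponsor chooses the score and the time point, and D, H.1 and J are made to agree on them.
- The sponsor chooses the missing-data method and states how deaths before the time point are handled, rather than letting them be imputed by default.
- Reconcile the exclusion in Section C, and the differing timing of randomisation in C, F, J, L and Table 1, with analysis by original group, so that no patient is removed after randomisation.
- State in K that randomised patients who drop out stay in the analysis even if they are replaced.
- Name an instrument for patient satisfaction, or take it out of the primary outcome.
- State whether the interim analysis tests this outcome. Only if it does, give an alpha boundary.

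The adjustment is there for precision; the comparison remains valid without it.

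The cost is wording in C, D, H.1, J and K and a little more analysis work. No new QLQ-C30 assessments are needed, since all five are already in Table 1. Satisfaction needs an instrument only if it is kept.

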### **H.1 Primary Outcome Measures:**

#### **a. Specific Aim 1**

Quality of life data will be assessed pre-operatively and at the post-operative visit.

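### The Aim 1 quality-of-life comparison uses one 6-month cross-section, so patients without that score contribute nothing and the scheduled baseline and earlier scores go unused

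*Combined protocol and SAP*

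**What the plan says.** All references are to the combined protocol and SAP.

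- **Outcome.** Section D: "The primary outcome measure for specific aim 1 will be the quality of life and patient satisfaction as measured by post-operative survey instruments". It gives no time point.
- **Analysis.** Section J: "Quality of Life measurements will be compared at 6 months, using descriptive statistics". No other QoL time point, model, baseline adjustment, missing-data rule or rule for death appears.
- **Collection.** In Table 1 (Section N) the row "Quality of Life Assessment" is marked at screening, the 2-week clinic visit, and 1, 3 and 6 months. Section H.3 lists the same post-operative contacts: "at the follow-up appointment (2 weeks following discharge), and at 1 month, 3 months, and 6 months (by telephone or mail").
- **A shorter schedule.** Section H.1: "Quality of life data will be assessed pre-operatively and at the post-operative visit".
- **Contact mode.** Section I: "The assessments at 1-month, 3-months, and 6-months will take place by mail and will not require a visit to the clinical site". Section H.3 also allows telephone.
- **Lost patients.** Section K replaces those who drop out or are lost to follow-up, to reach a minimum number that is still a placeholder. It does not mention death.
- **Analysis by group.** Section F: "once randomized, patients will be analyzed by the original group". This ends a sentence about cross-over. Section L repeats it in the same context.

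**The concern.** The plan asks patients for five QoL assessments and names one for analysis. That one comes latest, is obtained remotely, and follows an operation that Section B itself calls high-risk. Some deaths and unreturned forms by 6 months are foreseeable.

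Two things are at stake. The first is validity. Section C states that the trial cannot be blinded, so whether a patient replies may depend on both the arm and the recovery. A comparison of those who have a 6-month score is then no longer a comparison of the randomised groups. Recruiting replacements adds more patients with scores and does nothing about why the others lack them. The second is precision. Baseline and earlier scores predict the 6-month score, and a plain 6-month comparison discards that information even when non-response is balanced.

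**Working it through.** The plan states no sample size, SD, effect size, power or loss rate, so it has no figure to reproduce. Step 1 uses the documents. Steps 2 to 5 are illustrations on assumed values.

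**1. Collected against analysed.** Table 1 has one baseline and four post-operative QoL assessments. Section J names one of the four. A patient with baseline, 2-week, 1-month and 3-month scores but no 6-month score has four scores on file and no place in the comparison.

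**2. How many have a 6-month score.** Share = (1 − death) × (1 − non-return among survivors). Assumed: 5–15% dead, 10–30% not returned.

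| Death | Non-return | Share with score | Randomised per 100 scores |
|---|---|---|---|
| 5% | 10% | 0.95 × 0.90 = 0.855 | 100/0.855 → 117 |
| 10% | 20% | 0.90 × 0.80 = 0.720 | 100/0.720 → 139 |
| 15% | 30% | 0.85 × 0.70 = 0.595 | 100/0.595 → 169 |

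Replacement could reach 100 scores in each row, but the 100 would still all be surviving responders.

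**3. Bias with no true effect.** Let the mean of all patients be μ in both arms, the missing share m, and let missing patients score g points below responders. Then the responder mean is μ + g·m, and the spurious difference is g × (m_A − m_B).

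- g = 10, shares 5 percentage points apart: 10 × 0.05 = 0.5 points
- g = 20, shares 10 apart: 20 × 0.10 = 2.0 points
- g = 20, shares 15 apart: 20 × 0.15 = 3.0 points
- equal shares and equal g: 0

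The arm with more missing patients is flattered, whichever arm that is.

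**4. Precision with similar non-response.** Assumed 70 per arm, SD 20, non-response 22% and 19%. Scores available: 70 × 0.78 = 54.6 and 70 × 0.81 = 56.7. SE = 20 × √(1/54.6 + 1/56.7) = 3.8. A simulated likelihood analysis using all visits (adjacent-visit correlation 0.75) gave 3.5. The variance ratio is (3.8/3.5)² = 1.18, so the cross-section gives up roughly 18% in variance.

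**5. Bias with a true effect of 5 points, same settings.** This is a favourable case for the longitudinal model: non-response was driven by the 3-month score, which is the kind of missingness such a model handles. Each scenario had 600 simulated trials. The mean with no data missing was 5.2.

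| Non-response by arm | 6-month responders only | All visits |
|---|---|---|
| 22% vs 19% | 4.8 | 5.3 |
| 27% vs 18% | 3.3 | 5.3 |
| 34% vs 17%, stronger dependence | 1.1 | 5.3 |

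Other dependence coefficients (3,000 trials each) gave the same pattern: 4.6 against 5.0 (23% vs 20%), 2.4 against 5.0 (27% vs 18%) and −0.4 against 4.9 (35% vs 16%).

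Less favourable mechanisms (400 trials each) gave weaker recovery. If the same patients also miss the 3-month form, the all-visits estimate is 4.0 (29% vs 18%) or 2.3 (35% vs 16%). If non-response depends on the 6-month score itself, it is 3.3 (29% vs 18%) or 1.9 (35% vs 17%). It remained better than responders-only in these runs. Death was not simulated.

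**The case against.** The best reply is that a one-sentence plan is being read as a rule. Section J does not say that 6 months is the sole comparison or that patients without a form are dropped. That is correct: both are inferred from silence. The inference is still sound as a description of the stated method, because a descriptive 6-month comparison has no means of using a patient who lacks a 6-month score.

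A reader might also infer that the promise to analyse patients in their original group is broken. The documents do not support that. In Sections F and L the promise concerns cross-over, and a patient with a missing score has not been moved to another group.

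Nor do the documents show that a feeding benefit would be hidden. That needs more non-response among poorly recovering controls; the reverse pattern would exaggerate a benefit.

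Three further reservations stand. The count of earlier scores relies on Table 1 and Section H.3, while Section H.1 gives fewer and Section H routes QoL assessment through a separate protocol that is not available here. Telephone contact, which Section H.3 allows, may reduce non-response. And a 6-month comparison adjusted for baseline, with pre-specified missing-data sensitivity analyses, would also be defensible, though it would leave the intermediate scores unused.

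**Conclusion.** The point holds as a weakness in the choice of analysis that should be corrected before outcomes are seen. The documents establish that four post-operative QoL contacts are scheduled, one is named for comparison, no method lets a patient without that score contribute, and the only rule for lost patients is replacement.

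The size of any bias cannot be determined from the documents. On the assumed ranges it is 0 when missing shares and score gaps are equal between arms, and 0.5 to 3.0 points when shares differ by 5 to 15 percentage points and missing patients score 10 to 20 points lower. The loss of precision does not need differential non-response: about 3.8 against 3.5 in standard error, given 70 per arm, SD 20 and correlation 0.75. The simulated near-complete recovery of the true effect should be read as a favourable case, not as what a longitudinal model guarantees.

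**What to change.** Replace the Aim 1 sentence in Section J with:

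> All randomised patients with any post-operative QoL score are analysed in their randomised group in one mixed model for repeated measures (arm, visit, arm by visit, baseline QoL by visit, unstructured covariance) over 2 weeks, 1, 3 and 6 months. The primary contrast is the between-arm difference at 6 months, with its 95% confidence interval. Deaths and form return are tabulated by arm and visit. Sensitivity analyses give deaths the worst rank and allow missing scores to be worse than predicted.

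Six months is kept because it is the time point Section J names. The QLQ-C30 scale to which the model applies must also be named.

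In Section K, state that randomised patients who are lost stay in the analysis and are not replaced; allow for loss when the blank sample size is filled in. Reconcile the QoL schedule in Section H.1 with Section H.3 and Table 1, and the contact mode in Section H.3 with Section I. Add vital status to the existing contacts in Table 1.

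**Cost.** Plan wording, standard software and one extra data item; no new visits. The downside is that the model assumes missingness depends on observed scores and implicitly extrapolates QoL beyond death. The two sensitivity analyses are there to test those assumptions.
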